### 1.2. Secondary Objectives

- To assess safety in all patients and local regrowth rate and other cancer specific outcomes (disease-free survival [DFS], colostomy-free survival and overall survival [OS]) among patients assigned to organ preservation approach.
- To assess longitudinal functional outcomes and health-related quality of life [HRQOL] of this organ preservation approach.

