## 9. STUDY CALENDAR

Activity	Pre-study (to be performed within 45 days of enrollment unless otherwise specified)	RT	Chemo	Primary Outcome Assessment 8 (+/- 4) weeks after Chemo (Time 0)	Follow-up after Time 0 g		
					Every 3 months	Months 3, 6, 12, 18, 24	Months 6, 12, 18, 24
Pregnancy Test a	X						
Biopsy within 180 days of enrollment	X			X e	X e		
Clinical Exam with DRE b	X		X d	X	X		
Procto/Sigmoidoscopy within 90 days of enrollment	X		X d	X	X		
CT chest/abdomen/pelvis c	X		X d	X			X
MRI pelvis	X		X d	X		X	
Labs-CBCD, CMP, CEA	X		X i	X			X
ECOG	X						
HRQOL	X j			X			X f
PET/MRI or FDG-PET c	X			X			
AE evaluation	X j	X	X	X L	X f		
ctDNA	X j	X k		X		X h	

aNegative pregnancy test by urine, for women non-post-menopausal as defined in Appendix.

bDRE may be deferred for clinical reasons, as determined by treating physician.

cMRI abdomen can substitute for CT abdomen/pelvis per physician discretion; PET imaging is *optional*. PET/MRI is preferred.

dRestaging after 8 (+/-4) weeks of chemotherapy. Procto/sigmoidoscopy and CT CAP can be omitted per physician discretion.

eIf biopsy is needed to rule out residual or progressive tumor, per the discretion of the surgeon

fAfter TME, patients will leave surveillance schedule but continue to receive HRQOLs, and be assessed for treatment-related AEs

gFollow-up appointments and activities 2 weeks before and 2 weeks after each timepoint are permitted, and may be completed virtually.

hAmong only those managed with organ preservation

iCEA does not need to be collected; pre-study CBCD, CMP may suffice for cycle 1 Day 1 chemo labs

jActivities to be done after enrollment and before treatment begins

kctDNA will be collected following completion of RT

LAn additional AE evaluation may be scheduled up to 3 months after completion of chemotherapy if needed

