### 10.3 Exploratory Outcome Measures

- HRQOL in Appendices (B-H) will be collected by paper or electronically by the research coordinator at every study assessment visit or via mail or the myHealth messaging system (see Study Calendar). Data will be collected and stored in RedCap. Patients will receive 5 surveys (tailored to patient gender and the presence of a stoma). The entire functional assessment can be completed in less than 30 minutes, with an average of 15-20 minutes per patient.
  - Bowel function index (BFI)
    - We will use the 19-item BFI to assess bowel function. The psychometric properties of the instrument have been previously published and all subscales and total score show good internal consistency.
  - Low Anterior Resection Score (LARS)
    - All patients without a stoma will also complete 5 additional questions from the LARS. This is a validated 5 question index that was specifically developed to categorize bowel dysfunction after low anterior resection. In the LARS Score patients are asked to describe symptoms which best describe daily life. There is no specific time period, but at most the averages are over the past week. The LARS score has a range of 0-42 with 0-20 being No LARS, 21-29 being Minor LARS, and 30-42 being Major LARS.
  - Stoma QOL
    - We will also use the 21-item Stoma QOL for patients undergoing APR.
  - Sexual function
    - To assess sexual function, we will use gender-specific questionnaires: 5-item International Index of Erectile Function (IIEF-5) and 6-item Female Sexual Functioning Index.
  - Bladder function
    - Bladder function will be assessed using the International Prostate Symptom Score.
  - EuroQOL Group five dimensions Health Questionnaire (EQ-5D)
    - The EQ-5D is a widely used descriptive system of HRQOL states. It consists of five dimensions (mobility, self-care, usual activities, pain/discomfort, anxiety/depression) each of which can take one of five responses. The responses record five levels of severity (no problems/ slight problems/ moderate problems/ severe problems/ extreme problems or unable to function) within a particular EQ5D dimension. The EQ5D is almost always combined with a simple linear analogue

scale that asks respondents to rate their overall health on a vertical scale of 0 to 100.

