### **12.4 Primary Analysis**

#### **12.4.1 Analysis Population**

The analysis population will include all patients who initiated the RT and chemotherapy regimen (intent-to-treat). Patients who withdraw from the study prior to start of treatment will be replaced.

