### **12.5 Secondary Analysis**

#### **12.5.1 Analysis Population**

For the secondary outcome of local regrowth rate, the analysis population will include all patients managed with organ preservation approach. For the secondary outcomes of

toxicity, DFS, colostomy-free survival, OS and HRQOL, the analysis population will be the same set of patients included for the primary analysis.

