### **12.5.2 Analysis Plan**

For the toxicity outcome, we will calculate the proportion of patients meeting our definition of toxicity. In addition, we will present the frequency and percent of other adverse events reported in the study.

Local regrowth rate will be calculated as the proportion of patients with local regrowth based on the secondary analysis population. The local regrowth rate and its 95% confidence interval will be calculated.

Disease-free survival is defined as the time from start of RT therapy to date of progression or death due to any cause. If a subject is not known to have progressed or died, then DFS will be censored at the latest date the subject was known to be alive or disease-free (on or before the cut-off date). The DFS distribution will be estimated using the Kaplan-Meier method, and the Kaplan-Meier curves, medians and 95% confidence intervals of the medians will be presented.

Colostomy-free survival distribution will be estimated using the Kaplan-Meier method, and the Kaplan-Meier curves, medians and 95% confidence intervals of the medians will be presented.

OS is defined as the time from start of RT therapy to date of death due to any cause. If a subject is not known to have died, then OS will be censored at the latest date the subject was known to be alive (on or before the study end date). The OS distribution will be estimated using the Kaplan-Meier method, and the Kaplan-Meier curves, medians and 95% confidence intervals of the medians will be presented.

For the HRQOL measures, we will calculate the mean and standard deviations of each of the individual indices at baseline and every 3 months during the duration of the study; we will graphically depict scores at each time point. In addition, we will calculate the difference of the QoL scores at the baseline, time of cCR, and last follow up date and report summary statistics.

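### The supplementary HRQOL change score runs to an unfixed last follow-up date, and every HRQOL summary pools organ-preservation with TME patients; fixed visits and a descriptive split would fix both cheaply

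*Combined protocol and SAP*

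**What the plan says.** - **By-visit summary.** Section 12.5.2 first plans the "mean and standard deviations of each of the individual indices at baseline and every 3 months during the duration of the study", with scores graphed at each time point.
- **Change summary.** It then adds: "we will calculate the difference of the QoL scores at the baseline, time of cCR, and last follow up date and report summary statistics". It gives no visit, window or missing-data rule for the last of these three points.
- **Population.** Section 12.5.1 states that for "toxicity, DFS, colostomy-free survival, OS and HRQOL, the analysis population will be the same set of patients included for the primary analysis". Section 12.4.1 defines that set as everyone who began the regimen. No section splits HRQOL by whether the rectum was kept.
- **Objective.** Section 1.2: "To assess longitudinal functional outcomes and health-related quality of life [HRQOL] of this organ preservation approach".
- **Collection.** The Study Calendar (Section 9) schedules HRQOL before treatment, at Time 0 (the primary outcome assessment) and at months 6, 12, 18 and 24. Its footnote f adds: "After TME, patients will leave surveillance schedule but continue to receive HRQOLs". Section 4.2.5 ends QoL collection for patients who go on to treatment for progression, and ends on-study follow-up for everyone at 2 years.
- **Instruments.** Section 10.3: "All patients without a stoma will also complete 5 additional questions from the LARS". The same section gives the Stoma QOL to patients undergoing APR.

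**The concern.** There are two separate problems.

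**Timing.** A last score can be the Time 0 or month-6 value for one patient and the month-24 value for another. The difference in timing is not random, because one stated reason for an early last score is treatment for progression. The averaged change then belongs to no particular time, and its mix of times depends on how many patients progress and when.

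**Pooling.** The protocol itself expects function to differ between the groups being averaged. Section 2.1 describes worse body image, urinary symptoms and sexual function after APR, and puts bowel dysfunction after sphincter-sparing surgery at 50-90%. Section 2.2.1 gives better quality of life as a possible benefit of avoiding TME. A reader who wants to know how patients function with the rectum in place cannot get that from a pooled mean, and at the planned response rates most of the pooled patients will have had surgery.

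A lesser matter is that LARS means at successive visits can come from different respondents as stoma status changes. Section 2.2.2 mentions takedown of diverting ileostomies, so a stoma need not be permanent.

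**Working it through.** **1. The design figure behind the group sizes.** The HRQOL plan states no number of its own, so the relevant figure is the sample size in Section 12.6.2: null cCR 0.2, alternative 0.4, one-sided error 0.1, power 0.9, 17 then 20 patients, stop at 3 or fewer, reject the null at 11 or more of 37. An exact two-stage binomial search returns the same optimal Simon design (3/17, 10/37), with type I error 0.0948 and power 0.903. The 37 patients and the 20% to 40% range are therefore sound inputs.

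**2. How many patients keep the rectum.** Assume that preservation equals cCR and that everyone else has TME. With w the cCR rate, the number preserved is 37w.

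| cCR rate w | Preserved, 37w | TME, 37(1 − w) |
|---|---|---|
| 20% (null) | 7.4 | 29.6 |
| 11/37 = 29.7% (success threshold) | 11 | 26 |
| 40% (alternative) | 14.8 | 22.2 |

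**3. What pooling does to the change score.** Let D be the TME mean change minus the organ-preservation mean change.

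Pooled change = w × (preservation change) + (1 − w) × (TME change), so

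pooled change − preservation change = (1 − w) × D.

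This is 0.8D at 20%, 0.7D at 29.7% and 0.6D at 40%. D is not in the documents. For an assumed D of 5, 10 or 20 points, the gap is 4, 8 or 16 points at 20%, and 3, 6 or 12 points at 40%. The same weighting applies to the pooled by-visit means.

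**4. What the last-follow-up rule does.** Let f be the share of patients whose last score is at month 6, and G the difference between mean change at month 6 and at month 24. Compared with a mean in which everyone is measured at month 24, the shift is f × G. The documents give neither quantity. Assuming G = 10 points and f from 10% to 40%, the shift is 0.10 × 10 = 1 point up to 0.40 × 10 = 4 points.

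**5. Which summaries are affected.**

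| HRQOL summary in 12.5.2 | Mixes early and late times? | Pools preservation with TME? |
|---|---|---|
| Means, SDs and plots by visit | No | Yes |
| Difference at the time of cCR | No | Yes, unless limited to responders (12.5.2 does not say) |
| Difference at last follow-up | Yes | Yes |

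The by-visit summary is promised every 3 months, but the calendar has no HRQOL at months 3, 9, 15 or 21. In practice it rests on Time 0 and months 6, 12, 18 and 24.

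**6. LARS respondents.** Let s be the share of TME patients with a stoma, which the documents do not give. The number answering is 37 − 37(1 − w)s. For an assumed s of 10% to 50%, this is about 34 down to 22 at cCR 20%, and about 35 down to 26 at cCR 40%.

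**The case against.** **The by-visit means and plots already keep times apart.** This is right, and it limits the timing problem to one supplementary contrast. It would be wrong to infer that HRQOL is assessed only to the last follow-up. The by-visit summary does not address pooling, however.

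**Pooling fits a fair reading of the objective.** The synopsis describes the approach as a program that sends patients without cCR to TME. In Section 1.2 the first secondary objective ties cancer outcomes to patients assigned to organ preservation, and the HRQOL objective carries no such limit. A whole-program summary is therefore coherent, and the documents do not support saying that the pooled analysis fails its objective. What stands is that the pooled figure cannot also describe patients who keep the rectum. Section 12.5.1 already restricts local regrowth to that group, so a split is feasible.

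**LARS cannot sensibly be scored with a stoma.** Agreed. A reader might infer that stoma patients are data lost by design, or that the worst-off leave the LARS denominator and make function appear to improve. The documents support neither. LARS was built for bowel function after low anterior resection, and APR patients get the Stoma QOL. Section 2.1 attributes the 50-90% bowel dysfunction to sphincter-sparing surgery, whose patients are scored once they have no stoma. A within-patient LARS change also needs both scores. Only the shifting set of respondents behind the by-visit means remains, in an unknown direction.

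**A split conditions on response.** True. Differences between the groups would not isolate the effect of surgery, and groups of 7 to 15 are small. This argues for a labelled descriptive display, not for omitting it.

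**HRQOL is exploratory.** The synopsis and Section 10.3 say so, although Sections 1.2 and 12.5.1 list it with the secondary items. No decision rule uses it.

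**Conclusion.** The point holds as a modest improvement to the plan. The change score to last follow-up has no fixed time and mixes early with month-24 values in a way linked to progression. That affects this one contrast only.

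The pooling affects every HRQOL summary. If preservation equals cCR at the protocol's 20% to 40%, about 7 to 15 of 37 patients keep the rectum, and the pooled change misses theirs by 0.8 to 0.6 of any between-group difference. The preservation assumption is approximate. Section 4.2.5 requires multidisciplinary review before preservation, lets near-complete responders be observed further, and allows for later regrowth.

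The actual bias in points cannot be derived. The between-group difference, the share with early last scores and the stoma share are all assumed above. The direction of any LARS effect is unknown. The cCR result and the criteria in Section 12.7 are unaffected.

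**What to change.** In Section 12.5.2:

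1. Replace the last follow-up date with scheduled visits, months 12 and 24, and report within-patient change from baseline at each. State which visit the time of cCR denotes for a patient without cCR.
2. Keep the pooled by-visit means and plots as the whole-program summary, with visits matched to the Study Calendar.
3. Add a descriptive display by organ preservation versus TME, with stoma status shown for LARS, and give the number contributing at each visit.
4. State that the split is descriptive, because it conditions on response and the groups are small.

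Fixed visits do not recover scores missing after progression; they make the gap visible through the numbers contributing. No mixed model is required at this sample size.

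The cost is SAP wording and a few extra tables. The visits and questionnaires are already scheduled, and Section 10.3 already tailors forms to the presence of a stoma, so no new patients or visits are needed. The downside is imprecise means in small groups.

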## **12.6 Sample Size**

### **12.6.1 Accrual estimates**

We plan to enroll patients from radiation oncology, medical oncology, surgical oncology clinics as well as the GI multidisciplinary tumor board from 2020 to 2025. We estimate that 6 patients per month will be eligible for this study and that we will accrue 0-1 patients each month. We will allow patients to receive chemotherapy locally as prescribed by the trial and if necessary, can consider opening the trial at our satellite facilities to maximize our accrual numbers. If we do not meet our expected accrual rate, we will extend the study period and consider opening this trial at other institutions.

### **12.6.2 Sample size justification**

We plan to use a Simon 2 stage design to address our primary objective. Assuming a one-sided type one error of 0.1, power of 0.9, a null cCR of 0.2 versus an alternate cCR of 0.4, we plan to enroll a total of 37 patients. After 17 patients have been enrolled, we will assess the number of patients with cCR to determine whether to stop the study for futility or to continue. If less than or equal to 3 patients have cCR the study will be stopped. Otherwise, we will continue to enroll 20 more patients. The null hypothesis will be rejected if 11 or more total patients have cCR.

### **12.6.3 Effect size justification**

The historical rate for cCR based on previous literature is estimated to be ~20% based on data from randomized trials and systematic review and pooled analysis of 17 studies comprising 692 patients treated with a variety of neoadjuvant CRT approaches.

### **12.7 Criteria for future studies**

Based on our criteria stated above, if the study is not stopped at the interim analysis, if 11 or more patients of the 37 patients have cCR and 13 or fewer patients have grade 4+ non-hematologic toxicity, we will deem this treatment strategy acceptable.

## APPENDIX A: Menopausal Status

### Definition of Menopausal Status

Menopausal will be defined according to the following criteria:

#### **Post-menopausal:**

- Woman 60 years of age or older
- Woman aged 45-59 years with spontaneous cessation of menses for at least 12 months prior to registration
- Woman aged 45-59 years with cessation of menses for less than 12 months prior to registration AND an FSH level in the postmenopausal range (or >34.4 IU/L if institutional range is not available)
- Woman aged 45-59 years on hormone replacement therapy who have discontinued hormone replacement therapy at diagnosis of breast carcinoma and have an FSH level in the postmenopausal range according to institutional/laboratory standards (or 34.4 IU/L if the institutional range is not available)
- Prior bilateral oophorectomy
- Woman younger than 60 years of age who have had a prior hysterectomy (without bilateral oophorectomy) AND who have an FSH level in the postmenopausal range (or >34.4 IU/L if institutional range is not available)

**Pre- or peri-menopausal:** Not meeting definition for postmenopausal outlined

above.

## Appendix B: MSKCC Bowel Function Instrument

### MSKCC Bowel Function Instrument

Date: \_\_\_\_ / \_\_\_\_ / \_\_\_\_\_ (mm/dd/yyyy)      Patient Study ID: \_\_\_\_\_

As part of the SHiORT FOX trial, we are very interested in how your function (bowel, bladder, sexual) and quality of life. Below are 19 questions that should take less than 15 minutes to complete so that we can better understand how your life has been affected by rectal cancer therapy

Over the last 4 weeks....

	bowel movements/24 hours				
	Always	Most of the time	Sometimes	Rarely	Never
1. How many bowel movements did you generally have in 24 hours?	bowel movements/24 hours				
2. Do certain solid foods increase the number of bowel movements in a day?					
3. Do certain liquids that you drink increase the number of bowel movements in a day?					
4. Do you feel like you have totally emptied your bowels after a bowel movement?					
5. Do you get to the toilet on time?					
6. Do you have another bowel movement within 15 minutes of your last bowel movement?					
7. Do you know the difference between having to pass gas (air) and needing to have a bowel movement?					
8. Have you used medicines to decrease the number of bowel movements (drugs like Imodium®, Lomotil®)?					
9. Have you had diarrhea (no form, watery stool)?					
10. Have you had loose stool (slight form, but mushy)?					

	Always	Most of the time	Sometimes	Rarely	Never
11. Have you been able to wait 15 minutes to get to the toilet when you feel like you are going to have a bowel movement?					
12. Have you been able to control the passage of gas (air)?					
13. Have you limited the types of solid food you eat to control your bowel movements?					
14. Have you limited the types of liquids you drink to control your bowel movements?					
15. Have you had soilage (leakage of stool) of your undergarments during the day?					
16. Have you used a tissue, napkin, and/or pad in your undergarments during the day when you go to bed?					
17. Have you had soilage (leakage of stool) of your undergarments when you go to bed?					
18. How often have you had to alter your activities because of your bowel function?					
19. Compared to 4 weeks ago, how would you rate your bowel function now?					
	Much better than 4 weeks ago				
	Somewhat better than 4 weeks ago				
	About the same as 4 weeks ago				
	Somewhat worse than 4 weeks ago				
	Much worse than 4 weeks ago				

GOOD FUNCTION is HIGH

MSKCC Published Bowel Function Instrument	Coding Scheme	Subscale
1. Over the last 4 weeks, how many bowel movements do you generally have in 24 hours?	If < 2 score = 5 If $\geq 2$ and $< 3$ score = 4 If $\geq 3$ and $< 4$ score = 3 If $\geq 4$ and $< 5.5$ score = 2 If $\geq 5.5$ score = 1 Must reverse for scoring < 2 bm = 1 2 bm = 2 3 bm = 3 4 - 5.5 = 4 <math>\geq 5.5 = 5</math>	Frequency
2. Do certain solid foods increase the number of bowel movements in a day?	1=Always 5=Never	Diet
3. Do certain liquids that you drink increase the number of bowel movements in a day?	1=Always 5=Never	Diet
4. Do you feel like you have totally emptied your bowels after a bowel movement?	1=Never 5=Always	Separate
5. Do you get to the toilet on time?	1=Never 5=Always	Frequency
6. Do you have another bowel movement within 15 minutes of your last bowel movement?	1=Always 5=Never	Separate
7. Do you know the difference between having to pass gas (air) and needing to have a bowel movement?	1=Never 5=Always	Separate
8. Have you used medicines to decrease the number of bowel movements (drugs like Imodium®, Lomotil®)?	1=Always 5=Never	Frequency
9. Have you had diarrhea (no form, watery stool)?	1=Always 5=Never	Frequency
10. Have you had loose stool (slight form, but mushy)?	1=Always 5=Never	Frequency
11. Have you been able to wait 15 minutes to get to the toilet when you feel like you are going to have a bowel movement?	1=Never 5=Always	Frequency
12. Have you been able to control the passage of gas (air)?	1=Never 5=Always	Separate
13. Have you limited the types of solid food you eat to control your bowel movements?	1=Always 5=Never	Diet
14. Have you limited the types of liquids you drink to control your bowel movements?	1=Always 5=Never	Diet
15. Have you had soilage (leakage of stool) of your undergarments during the day?	1=Always 5=Never	Urgency/soilage
16. Have you used a tissue, napkin, and/or pad in your undergarments during the day in case of stool leakage?	1=Always 5=Never	Urgency/soilage
17. Have you had soilage (leakage of stool) of your	1=Always 5=Never	Urgency/Soilage

undergarments when you go to bed?		lage
18. How often have you had to alter your activities because of your bowel function?	1=Always 5=Never	Urgency/Soilage
19. Compared to 4 weeks ago, how would you rate your bowel function now?	1=Always 5=Never	Separate

For question 1, high scores indicate good bowel function.

Questions 4, 5, 7, 11, and 12 are bolded to indicate reverse scoring codes (1=Never, 5=Always).

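### Item 16 on the Appendix B patient bowel form is misprinted and does not match the item that the scoring table scores in the urgency/soilage subscale

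*Combined protocol and SAP*

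**What the plan says.** Section 10.3 lists health-related quality of life as an exploratory outcome and names the bowel instrument: "We will use the 19-item BFI to assess bowel function". It supports that choice by reference to validation work: "The psychometric properties of the instrument have been previously published and all subscales and total score show good internal consistency". Section 1.2 also names longitudinal functional outcomes and quality of life among the secondary objectives.

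Appendix B gives the instrument twice: as the form for patients, and as a scoring table with a code and a subscale label for each item. The patient form prints item 16 as "Have you used a tissue, napkin, and/or pad in your undergarments during the day when you go to bed". The scoring table prints item 16 as "Have you used a tissue, napkin, and/or pad in your undergarments during the day in case of stool leakage", codes it from 1 (always) to 5 (never), and labels it urgency/soilage.

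The planned analysis, in section 12.5.2, is descriptive: "For the HRQOL measures, we will calculate the mean and standard deviations of each of the individual indices at baseline and every 3 months", together with differences between baseline, the time of cCR and last follow-up. No hypothesis test is planned on these scores.

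**The concern.** The form's item 16 sets two time frames against each other, daytime and going to bed. A patient could answer for the day, for the night, or for both. The form also drops the link to stool leakage. Without it, pad use for another reason, such as urinary leakage or menstruation, fits the question as printed. Both are plausible here: section 10.3 measures bladder function separately, and the eligibility checklist in section 3.1 admits women of childbearing potential.

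If the plan is followed as written, answers to this question are coded as though they answered the scoring-table item. The validation cited in section 10.3 belongs to the published instrument, and it cannot be assumed to carry over to an item with different content. The stake is modest but relevant to the trial's rationale: section 2.1 names soiling and incontinence among the harms of sphincter-sparing surgery, and section 2.2.1 argues that organ preservation may improve quality of life.

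**Working it through.** No sample-size or error-rate figure is involved. The check compares wording and counts items.

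**1. Item count.** Section 10.3 gives 19 items. The subscale labels in the Appendix B scoring table give:

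- Frequency: items 1, 5, 8, 9, 10, 11 (6 items)
- Diet: items 2, 3, 13, 14 (4 items)
- Urgency/soilage: items 15, 16, 17, 18 (4 items)
- Separate: items 4, 6, 7, 12, 19 (5 items)

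6 + 4 + 4 + 5 = 19, which reproduces the stated figure. Item 16 is one of four items in its subscale.

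**2. Wording of the four urgency/soilage items, form against scoring table.**

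- Item 15: "Have you had soilage (leakage of stool) of your undergarments during the day". Same in both places.
- Item 16: the form has "Have you used a tissue, napkin, and/or pad in your undergarments during the day when you go to bed"; the table has "Have you used a tissue, napkin, and/or pad in your undergarments during the day in case of stool leakage". They differ in two ways: the form adds a conflicting bedtime frame, and it omits the leakage reason.
- Item 17: "Have you had soilage (leakage of stool) of your undergarments when you go to bed". Same in both places.
- Item 18: "How often have you had to alter your activities because of your bowel function". Same in both places.

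So 3 of 4 items match as printed, and 4 of 4 would match after correction. Outside the subscale, item 1 differs only trivially between the two lists. Nothing in the protocol reconciles the two wordings of item 16 or says how to score the form's wording.

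**3. Likely origin.** The stray ending on item 16 is the same as the ending of item 17, in the row directly below. Item 17 is complete in its own row, so its words were repeated rather than displaced. The leakage reason given in the scoring table does not appear in item 16 on the form. This looks like a copying slip in the form. A fault in converting the table from PDF is possible but less likely.

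**4. Ceiling on the effect.** *Assumption: each subscale is the simple sum of its items, each scored 1 to 5.* The appendix gives codes and labels but no summation rule for this instrument.

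- Subscale minimum: 4 × 1 = 4. Maximum: 4 × 5 = 20. Range: 20 − 4 = 16.
- Largest possible movement from item 16: 5 − 1 = 4.
- Share of the subscale range: 4 / 16 = 25%.
- If all 19 items were summed: range 19 × (5 − 1) = 76, and the share is 4 / 76 = about 5%.

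**5. Exposure.** The study calendar schedules quality of life at baseline, Time 0 and months 6, 12, 18 and 24, which is up to 6 occasions per patient. Section 12.5.2 instead describes summaries every 3 months. Section 4.2.5 stops questionnaires for patients who are treated for progression.

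**The case against.** The strongest reply is that the item is garbled but not useless. It still refers to the day and still asks about a tissue, napkin or pad. It also sits between two items that mention leakage of stool, so many patients would infer what was meant. That stands, and it sets the limit of the point.

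A reader might draw four stronger conclusions that the documents do not support.

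- **That the item cannot be interpreted, or has become a night-time item.** The daytime phrase is still printed. What can be said is that an answer cannot be assigned with confidence to day or night, or tied to leakage.
- **That the scores as a whole are no longer the published measure and cannot be compared with other series.** The Frequency and Diet subscales are unaffected, and three of the four urgency/soilage items match. Loss of comparability beyond this subscale, or a total containing item 16, is not shown.
- **That every completed form carries the error.** Section 10.3 allows paper or electronic collection, and only the appendix form is shown. The wording of the electronic survey is unknown.
- **That scores shift by 4 points.** This is a ceiling under an assumed summation rule. It would need a patient to move from one end of the response scale to the other purely because of how the question is read. The documents give no basis for a typical shift.

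It may also be said that the same misprint at every visit cancels out in within-patient change. It need not, because a patient may read an ambiguous question differently on different occasions. The LARS questionnaire in Appendix C asks about leakage of liquid stool and gives partial cover, but it does not ask about pad use and is given only to patients without a stoma.

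**Conclusion.** The point holds as a misprint in a data-collection form. Item 16 on the Appendix B patient form differs in content from the item that the scoring table scores, and its answers cannot safely be treated as answers to that item. The reach is item 16, the four-item urgency/soilage subscale and any total that includes item 16. Under a simple-sum assumption that the protocol does not state, the ceiling is one quarter of the subscale range; the actual effect is unknown and may be small.

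The cCR endpoint, the two-stage design, the futility and toxicity rules and the other bowel subscales are unaffected. The outcome is listed as exploratory and its analysis is descriptive. This is a minor correction, worth making because the right wording is already in the sponsor's own appendix. The conclusion rests on the printed appendix being what patients receive, which the sponsor should confirm.

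**What to change.** 1. Compare the Appendix B form with the source document, the paper form in use and the electronic survey, to establish which of them carry the misprint.
2. Where it is present, replace item 16 with the scoring-table wording: "Have you used a tissue, napkin, and/or pad in your undergarments during the day in case of stool leakage".
3. Record the date of correction for each mode of collection, and flag forms completed on the misprinted wording.
4. For flagged forms, report the urgency/soilage subscale with and without item 16. Do not prorate unless a rule is specified in advance. The only proration rule in the appendices belongs to the stoma scale in Appendix D, and none is given for the bowel instrument.
5. State how the subscale and any total are formed from the items, so that the two summaries are defined.

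The cost is one line on the form and, if affected, in the survey, plus notification of the IRB and a short additional summary. Where the misprint was used, the sponsor also accepts that item 16 answers already given cannot be repaired.
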